#### 7.3.2.4 Toxicology

Single oral administration of E7438 up to 1000 mg/kg was tolerated in SD rats and cynomolgus monkeys.

In a 4-week repeated-dose toxicity study in rats, a number of animals were found dead possibly due to the gastrointestinal tract toxicity at a dose of 1000 mg/kg/day between Day 7 and Day 21. Pathological changes were found in these animals in the gastrointestinal tract (glandular stomach mucosa erosion/ulceration and glandular stomach and gastrointestinal epithelia degeneration/necrosis) and other organs such as kidney (eosinophilic droplets and necrosis in epithelial cells), bone marrow (slight-to-moderate hypocellularity), lymphoid tissues (lymphoid depletion), and new trabecular bone formation in the medullary cavity of the sternum and femur. In some rats at 1000 mg/kg/day, there were secondary clinical laboratory changes or changes possibly due to general deterioration. Reversibility or recovery trend of all adverse findings observed at 1000 mg/kg/day was demonstrated after a

2-week off-dose period subsequent to cessation of dosing in surviving animals at 1000 mg/kg/day on Day 21 or later. While a drop of urinary sediment was observed at doses of 100 and 300 mg/kg, no pathological changes were found in the urinary system. In the 13-week repeated-dose toxicity study, there was an occurrence of lymphoblastic lymphoma originated from the thymus in the 300 mg/kg group or higher doses. Lymphoma was the cause of death or moribundity after Day 65. A total of 3/20 males and 8/20 females at 300 mg/kg, and 1/20 male and 0/20 female at 600 mg/kg developed lymphoblastic lymphoma in the study. Metastases to various tissues and organs included. At 600 mg/kg, findings other than lymphoma were lymphoid depletion, shortening of the lower incisor, trabecular formation in the femur and sternum, erosion/ulcer and regenerative changes in the upper gastrointestinal tract, and granular materials in the renal pelvis. Changes at 300 mg/kg/day were similar to but less severe than those observed at 600 mg/kg/day. At 100 mg/kg/day, there were no significant changes except for labial abscess observed at 300 mg/kg/day or higher doses in one male rat. For the recovery evaluation, primary non-neoplastic changes were generally reversible with the exception of splenic lymphoid depletion and changes in the bone and incisors after the 4-week recovery period.

In a 4-week repeated-dose toxicity study in cynomolgus monkeys, the 1000-mg/kg dose was discontinued on Day 8 or Day 9 of dosing due to adverse clinical observations, which resulted in the euthanasia of 3 moribund animals. On Day 11 or Day 12, dosing was re-initiated at a lower dose of 600 mg/kg/day for surviving animals. During the dosing period, 1000 mg/kg/day caused infrequent and intermittent emesis on Day 6 after the morning dose only. There were no test article-related effects on heart rate or electrocardiograms (ECGs) observed in this study. In moribund animals at 1000 mg/kg/day, there were adverse clinical signs and associated decreased muscle tone on Day 7, clinical pathology abnormalities, and changes in the gastrointestinal tract and liver, however, the cause of morbidity in these animals was not clearly identified. In both the moribund animals at 1000 mg/kg and the remaining high-dose animals that had their dose reduced to 600 mg/kg, there were test article-related changes in the liver and kidney as well as an increase in alanine aminotransferase (ALT) and triglycerides. At 300 mg/kg and above, lymphoid depletion, that was dose-dependent in incidence and severity was observed. Reversibility or a trend towards reversibility for toxicity was demonstrated in one 1000-mg/kg/day animal after a 21-day recovery period. In the 13-week cynomolgus monkey study, the principal clinical and necropsy findings in the 13-week monkey study were similar to those observed in a 4-week study, although more pronounced. Moribundity occurred in a single female animal at 600 mg/kg/day on Day 83 following severe clinical signs (decreased activity, cold to touch, hunched posture, and shivering/tremor). While the cause of moribundity was not clearly explained by histopathology, E7438-related significant changes in this animal were similar to those observed in terminal sacrificed animals as below. E7438-related clinical observations included emesis and abnormal feces. The incidence of emesis and/or fecal changes was sporadic in all tazemetostat-treated groups; however, the incidence of emesis was dose related. At 300 mg/kg/day and above there was a mild shortening of the RR interval, which was not statistically significant. Dose-dependent lymphoid depletion in the spleen, lymph nodes, and thymus, increases in ALT and AST, hepatocyte hypertrophy, Kupffer cell hypertrophy/pigmentation, and bile duct hyperplasia in the liver were observed. At 600 mg/kg/day there were increases in ALP and glomerulopathy and tubular pigmentation in

the kidney. No toxicologically significant changes were observed at 100 mg/kg/day. After a 4-week recovery, there was a trend toward reversibility in most parameters; however, the 4-week recovery period was not sufficient for complete assessment of reversibility for some changes.

E7438 was not genotoxic in an in vitro bacterial reverse mutation assay, in vitro micronuclei assay, and in vivo rat micronuclei studies.

In a repeated-dose, range-finding study in juvenile SD rats, E7438 was initiated at Post-Natal Day 7 and repeatedly administered for 4 weeks. All male and female animals treated at 500 and 1000 mg/kg euthanized following clinical signs of hypoactivity and a cool and/or pale body after first or second dosing. Histopathological changes were limited to the stomach, hematopoietic and lymphoid tissues, and kidney. The gastric toxicity was considered to be the cause of moribundity. No toxicologically significant changes were found at 50 and 150 mg/kg/day.

The ultraviolet (UV) absorption spectrum of E7438 showed absorption maxima at 302 nm and 265 nm was observed. Thus, an in vitro phototoxicity study of E7438 in 3T3 cells was performed. E7438 showed phototoxic potential because Mean Photo Effect, known as phototoxicity index, was more than the criterion for phototoxic, 0.15 (0.270 and 0.347) when examined up to the solubility limit of 100 µg/mL.

In a 13-week repeated-dose rat toxicity study with a 4-week recovery period, there was an occurrence of lymphoblastic lymphoma originated from the thymus. To investigate further the mechanism of lymphomagenesis noted in this study, additional 13-week rat studies were completed using two structurally similar, but chemically distinct EZH2 inhibitors, EPZ-10961 and EPZ011989. They have similar specificity and mechanism of inhibition and inhibit cellular H3K27Me3 with 3 to 4-fold higher potency than E7438. Non-dose dependent incidence of lymphoma was observed in studies for EPZ-10961 and EPZ011989 in approximately the same time frame that it was seen in the 13-week rat study with E7438 (after 8-10 weeks of dosing). Immunophenotyping of cells isolated from the thymus, bone marrow, and spleen samples showed higher percentages of CD8+ T-cells and  $\alpha\beta$  TCR+ T-cells and lower percentage of CD4+ T-cells and  $\gamma\delta$  TCR+ T-cells in thymus derived samples. In contrast, immunophenotyping of cells isolated from the thymus, bone marrow, and spleen samples from rats without lymphoma showed lower percentages of  $\alpha\beta$  TCR+ T-cells and concurrent higher percentage of  $\gamma\delta$  TCR+ T-cells. The similar results were obtained with EPZ-10961. Notch-mediated transcription was studied in thymus samples from E7438 or the EPZ011989 study. The mechanism of lymphomagenesis in these rats does not appear to be related to E7438-mediated alterations in the Notch signaling pathway or effects on retroviral reintegration of the Rat Leukemia virus (RaLV). Gene expression and whole transcriptome analysis from thymus tissue isolated during studies with EPZ011989 revealed elevated expression of *Myc* in rats with lymphoma, but otherwise, no similarities to genetic and transcriptional abnormalities related to mechanism of occurrence and immunophenotyping in human T-cell acute lymphoblastic leukemia were seen.

An additional 4-week oral study in rats was performed with E7438 to assess the toxicologic impact of the presence of new impurities in the lot to be used in the clinical study of

tazemetostat in tablet form. No notable changes attributable to new impurities were observed.

### 7.3.3 Clinical Studies

As of the cutoff date of 15 Jan 2016, the following 3 studies are ongoing outside Japan.

- Study E7438-G000-101, “An Open-Label, Multicenter, Phase 1/2 Study of E7438 (EZH2 Histone Methyl Transferase [HMT] Inhibitor) as a Single Agent in Subjects with Advanced Solid Tumors or with B-cell Lymphomas”
- Study EZH-102 “A Phase 1 Study of the EZH2 Inhibitor Tazemetostat in Pediatric Subjects with Relapsed or Refractory INI1-Negative Tumors or Synovial Sarcoma”
- Study EZH-202 “A Phase 2, Multicenter Study of the EZH2 Inhibitor Tazemetostat in Adult Subjects with INI1-Negative Tumors or Relapsed/Refractory Synovial Sarcoma”

Eighty-eight subjects had been enrolled in Study E7438-G000-101 and 1 subject in study EZH-202, all of whom, a total of 89 subjects, had been exposed to tazemetostat.

Seventy-eight of 89 (87.6%) subjects experienced at least 1 AE and 51 of 89 (57.3%) subjects experienced AEs that were considered related to tazemetostat by the investigator. AEs occurring in  $\geq 5\%$  of subjects and in descending order of frequency were asthenia (34.8%), nausea (15.7%), thrombocytopenia (14.6%), decreased appetite (13.5%), anemia (12.4%), constipation (12.4%), dysgeusia (7.9%), vomiting (7.9%), diarrhea (6.7%), dry skin (6.7%), dyspnea (6.7%), muscle spasms (6.7%), abdominal pain (5.6%), and neutropenia (5.6%). Of the subjects who experienced related AEs, the majority reported Grade 1 or 2 events. Seven subjects (7.9%) experienced Grade 3 or 4 AEs and 5 subjects (5.6%) discontinued study drug due to AEs.

One subject experienced Grade 4 thrombocytopenia during the dose-escalation group of Study E7438-G000-101 at the dose level of 1600 mg BID; this event was also considered to be a DLT. The protocol-defined MTD was not reached. No other DLTs were observed.

Twenty-two of 89 subjects experienced 31 serious adverse events (SAEs). Of these, 4 SAEs occurring in 3 subjects were considered possibly related to study drug (anemia, thrombocytopenia, and 2 events of neutropenia). In Study E7438-G000-101, 11 subjects died. For 9 subjects, the cause of death was progressive disease, 1 was due to an AE, and 1 was noted as being not due to progressive disease (no further information was available at the time of data cutoff [15 Jan 2016]).

The clinical PK characteristics of tazemetostat are derived from Study E7438-G000-101 in which tazemetostat was administered at doses of 100 mg BID as a suspension or tablet formulation and 200, 400, 800, and 1600 mg BID as a tablet formulation. Tazemetostat was rapidly absorbed with a time to the maximum plasma concentration ( $t_{max}$ ) of approximately 1 to 2 hours postdose and a mean  $t_{1/2}$  of approximately 3 to 5 hours. After multiple dosing, there was a dose-dependent decrease in tazemetostat systemic exposure relative to Day 1. However, no further reduction in systemic exposure was observed beyond Day 15.

Administration of tazemetostat with a high-fat meal decreased geometric mean  $AUC_{(0-inf)}$  and  $C_{max}$  values approximately 7% and 28%, respectively, relative to administration in the fasted state. Administration of tazemetostat with a high-fat meal also resulted in a 4-fold increase in median  $t_{max}$  relative to administration in the fasted state. All individual  $C_{max}$  and  $AUC_{(0-inf)}$  values observed after administration of tazemetostat following a high-fat meal were within the range of the respective values observed after administration in the fasted state. The decrease in systemic exposure is not clinically significant, and therefore tazemetostat can be taken without regard to meals.

Tazemetostat antitumor activity has been evaluated in Phase 1 part of Study E7438-G000-101. As of 07 Nov 2015, tazemetostat has demonstrated antitumor activity in subjects with B-cell lymphomas and INI1- and SMRCA4-negative cancers. Objective responses (2 CRs and 7 PRs) have been observed in 9 of 16 response evaluable subjects (DLBCL [5 of 12]; FL [3 of 4]; and marginal zone lymphoma [1 of 1]). Objective responses (1 CR and 3 PRs) were also observed in 4 of 11 response evaluable subjects with INI1- and SMARCA4-negative cancers (MRT) [2 of 5]; epithelioid sarcoma (ES) [1 of 3]; malignant rhabdoid tumor of the ovary (MRTO) [1 of 2]).

Phase 1 data were reviewed by an Independent Data Monitoring Committee on 12 Nov 2014. The committee agreed that the recommended Phase 2 dose be 800 mg BID based on evaluation of safety, PK, biomarker, and antitumor activity.

## 7.4 Study Rationale

This study is the Japan Phase 1 study to investigate the tolerability, safety, PK, and preliminary antitumor activity of tazemetostat in patients with relapsed or refractory B-cell NHL. The tolerability and safety of tazemetostat in Japanese patients has not yet been investigated; therefore, this study was planned.

Tazemetostat 800 mg will be administered orally by single dose in Cycle 0 and by continuous 800 mg BID in Cycle 1 and later in 28-day cycles. Tazemetostat treatment will continue until disease progression, development of unacceptable toxicity, subject requests to discontinue, withdrawal of consent, or study termination by the sponsor.

In the Phase 1 part of the Study E7438-G000-101, a Phase 1/2 study currently ongoing outside Japan, the recommended dose of tazemetostat has been determined to be 800 mg BID. The Phase 2 part of the study is ongoing at this dose level. Safety and tolerability of tazemetostat for subjects enrolled in Study E7438-G000-101 was assessed as of 15 Jan 2016. Tazemetostat was administered twice daily in 6 subjects for 100 mg, 3 subjects for 200 mg, 16 subjects for 400 mg, 46 subjects for 800 mg (including 1 subject from Study EZH-202), and 18 subjects for 1600 mg. One subject experienced treatment-related Grade 4 thrombocytopenia at the dose level of 1600 mg BID; this event was also considered to be a DLT. The protocol-defined MTD was not reached. Treatment-related Grade 3 or 4 AEs observed at 800 mg BID were thrombocytopenia (2 subjects, 4.3%) and Grade 3 hepatocellular injury and Grade 3 hypertension (1 subject each, 2.2%) while no treatment-related Grade 3 or 4 AEs occurred at the dose level of 400 mg BID or lower doses. Based on

the current clinical data, the starting dose of 800 mg, half of the maximum single dose of 1600 mg established outside Japan, was considered as suitable for this study whereas clinical data in Japanese subjects are not available.

Tazemetostat has demonstrated antitumor activity in subjects with B-cell lymphomas in Study E7438-G000-101. As of 07 Nov 2015, objective responses (2 CRs and 7 PRs) have been observed in 9 of 16 response evaluable subjects. Therefore, the target population of this study is considered to be relapsed or refractory B-cell NHL, in which preliminary efficacy is expected.

With these reasons, the Phase 1 study was designed to investigate the tolerability, safety, PK, and preliminary anti-tumor activity of tazemetostat in Japanese patients with relapsed or refractory B-cell NHL, and the current study is rationalized.

## 8 STUDY OBJECTIVES

### 8.1 Primary Objective

To assess the tolerability of tazemetostat in patients with B-cell non-Hodgkin's lymphoma (NHL).

### 8.2 Secondary Objectives

- (1) To assess the safety of tazemetostat.
- (2) To assess the PK profile of tazemetostat.
- (3) To assess the preliminary anti-tumor activity of tazemetostat.

### 8.3 Exploratory Objectives

CCI

[figure not shown]
## 9 INVESTIGATIONAL PLAN

### 9.1 Overall Study Design and Plan

This is a multicenter, single-arm, phase 1 study to assess the tolerability, safety, PK and preliminary anti-tumor activity of tazemetostat in patients with relapsed or refractory B-cell NHL.

#### 9.1.1 Study Design

The study design of this study is presented in Figure 1. This study will be conducted in the following 4 phases: Pre-treatment Phase, Treatment Phase, Extension Phase, and Follow-up Phase.

**Figure 1 Study Design**

BID = twice daily, DLT = dose limiting toxicity.

##### 9.1.1.1 Pre-treatment Phase

The Pre-treatment Phase will last no longer than 28 days and include a period to obtain informed consent, screening, enrollment, and a baseline assessment. Informed consent will be obtained after the study has been fully explained to each subject and before the conduct of any screening procedures or assessments. After screening assessments, the patient who meets the inclusion criteria and does not meet the exclusion criteria will be enrolled. The baseline assessment will be conducted within 3 days before the treatment in order to confirm

that the patient continues to meet the inclusion criteria and does not meet the exclusion criteria before moving to the Treatment Phase.

The CRF must be completed to indicate whether the subject is eligible to participate in the study and to provide reasons for screen failure, if applicable.

#### 9.1.1.2 Treatment Phase

The Treatment Phase consists of Cycle 0 (4 days) for tazemetostat single-dose oral administration and Cycle 1 of 28 days for tazemetostat twice daily (BID) oral administration on a continuous basis. The subject who discontinues study drug during the Treatment Phase will have a discontinuation visit of the Follow-up Phase. The subject who completes the Treatment Phase will enter the Extension Phase.

Considering visit schedule and safety, subjects will be hospitalized from Cycle 0/Day 1 (C0D1) to Cycle 1/Day 15 (C1D15). Based on the thorough evaluation of the data obtained on C1D15 and all safety data available, the investigator or subinvestigator will determine whether subjects can be treated on an outpatient basis. When subjects are considered to require extended hospitalization to ensure subject safety, they will be hospitalized from C1D15 onwards.

#### 9.1.1.3 Extension Phase

The Extension Phase consists of Cycle 2 of 28 days and later for tazemetostat BID oral administration on a continuous basis and lasts until discontinuation of study drug. Informed consent should be obtained before initiating the study or before entering the Extension Phase when Cycle 2 or later administrations will be continued. Subjects will discontinue study drug at the time of disease progression, development of unacceptable toxicity, subject's request to discontinue, withdrawal of consent, or study termination by the sponsor. The subject who discontinues study drug during the Extension Phase will have a discontinuation visit of the Follow-up Phase.

#### 9.1.1.4 Follow-Up Phase

The Follow-up Phase consists of the evaluation at discontinuation which is performed within 7 days after the discontinuation of the study and a final observation which occurs 30 days (+7 days) after final administration of tazemetostat or initiation of a new anti-tumor therapy, whichever occurs early.

### 9.1.2 Dose-Limiting Toxicities (DLT)

The starting dose of tazemetostat is 800 mg as a single dose (Cycle 0) and 800 mg BID as continuous dosing (Cycle 1 and later). Three subjects will be enrolled and ensure that they are evaluable for dose-limiting toxicities (DLTs) at the end of Cycle 1 of the cohort. When a DLT is observed in 0 or 1 of 3 subjects at a given dose level, 3 additional subjects would be treated at the same dose level. When 2 of 3 subjects at a given dose level experience DLTs, enrollment of additional subjects will be discussed jointly by the investigator and sponsor.

The opinion of Independent Data Monitoring Advisor should be also obtained. When additional subjects are to be enrolled, they will be monitored individually. When no DLTs are observed, up to 3 additional subjects will be enrolled. When no additional subjects are accrued or 3 subjects in total experienced DLTs, the enrollment in the cohort will be discontinued and the lower dose level of tazemetostat cohort will be considered jointly by the investigator and sponsor. The opinion of Independent Data Monitoring Advisor can be obtained if needed.

If the subject is regarded as DLT non-evaluable (eg, early discontinuation due to non-DLT, medication compliance with <75% in Cycle 1 as a result of the reason other than treatment related toxicity), another subject will be added for replacement.

A DLT is defined as toxicity related to study drug in Table 1 below. The tolerability of tazemetostat will be determined based on the incidence of DLTs in Cycles 0 and 1. If DLTs occur in 0 or 1 of 6 subjects, this dose level is considered tolerable. If DLTs occurs in 2 of 6 subjects, the tolerability of this dose level will be determined jointly by the investigator and sponsor. The opinion of Independent Data Monitoring Advisor should be also obtained. In the case of difficulty of determination of whether a subject should be counted as having experienced a DLT and/or not for tolerability assessment, the final determination will be made jointly by the investigator and sponsor. The opinion of Independent Data Monitoring Advisor can be obtained if needed.

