**Table 1 Dose-Limiting Toxicities (DLT)**

Toxicity Category	Toxicity/CTCAE Grade
Hematological Toxicity	
 
• Grade 4 neutropenia for > 7 days or neutropenia requiring hematopoietic growth factors
 
• ≥ Grade 3 febrile neutropenia
 
• Grade 4 thrombocytopenia, Grade 3 thrombocytopenia with bleeding, or thrombocytopenia requiring platelet transfusion
 
• Grade 4 anemia or anemia requiring erythrocyte transfusion
 

Non-hematological Toxicity	
 
• ≥ Grade 3 nausea, vomiting, or diarrhea that persists > 7 days despite maximal medical therapy
 
• ≥ Grade 3 non-hematological laboratory abnormalities with clinical symptoms that persists > 7 days
 
• Other Grade 3 toxicity lasting > 7 days or Grade 4 non-hematological toxicity of any duration
 

Medication compliance	
 
• Failure to administer ≥ 75% (≥ 42/56 doses) of the planned administration number of study drug in Cycle 1 as a result of treatment-related toxicity
 

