**Table 6 Schedule of Procedures/Assessments in Study E7438-J081-106 (EZH-106)**

Phase	Pre-treatment		Treatment						Extension		Follow-up	
Period	Screening a	Baseline	Cycle 0	Cycle 1					Cycle 2 and later		Discontinuation	Final observation
Day	Within 28 days before administration	Within 3 days before administration	1	1 b	3	8 (±1)	15 (±1)	22 (±1)	1 (±3) c	15 (±3) n	(+7)	30 days after last dosing (+7) d
Informed Consent	X								[X] m			
Demographic data	X											
Inclusion/exclusion Criteria	X	X										
Medical history/Current medical condition	X											
Previous therapy	X											
Height	X											
Body weight	X	X		X		X	X	X	X	X	X	
Physical examination	X	X	X	X		X	X	X	X	X	X	X
Vital signs	X		X	X		X	X	X	X	X	X	X
ECOG-PS	X	X		X					X		X	
12-lead ECGs e	X		X	X			X		X	X	X	
Echocardiogram or MUGA scan f	X								[X]			
Pregnancy test (if applicable)	X										X	
Virus test	X											
Hematology o	X	X		X		X	X	X	X	X	X	X
Blood chemistry	X	X		X		X	X	X	X	X	X	X
Urinalysis	X	X		X		X	X	X	X	X	X	X
PK (blood) g			X		X	X	X	X	[X]			
PK (urine) h			X				X					
Tumor assessments (CT) i	X									[X]	X	
Bone marrow aspiration or biopsy j	X									[X]		
Tazemetostat administration k			X	Continuous 28-day cycle of tazemetostat twice daily.								
Archival tumor sample submission l				X								
Adverse events				From informed consent to final observation								

Concomitant drug/therapies	From informed consent to final observation
----------------------------	--

Note, [X]: In case to perform.

C#/D# = Cycle #/Day #, CR = complete response, CT = computed tomography, ECG = electrocardiogram, ECOG-PS = Eastern Cooperative Oncology Group-Performance Status, MUGA = multigated acquisition, PK = pharmacokinetics.

a: Screening assessments may be used as baseline assessments if performed within 3 days of the first administration of study drug.

b: To start C1D1 on Cycle 0 Days 4-9.

c: +1 day for C2D1.

d: When subject needs to receive other anti-tumor therapy due to deterioration of the disease within 30 days after the final study drug administration, final observation must be conducted before initiation of other anti-tumor therapy and the data within 7 days before next anti-tumor therapy can be used for final observation. .

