e: 12-Lead ECGs on C0D1, C1D1, and C2D1 will be collected at pre-dose and 0.5-2 hours post dose of first administration.

f: Echocardiogram or MUGA scan will be performed at screening, every 16 weeks (ie, Day 1 of every 4 cycles [ $\pm$  1 week]) from C2D1. Additional assessments may be performed if clinically indicated.

g: Blood samples for PK analyses of tazemetostat and metabolites will be collected in C0D1 at predose, 0.5, 1, 2, 4, 6, 8, 10, 12, 24, 48 and 72 hours postdose; C1D3 and C1D8 at predose of first administration; C1D15 at predose of first administration, 0.5, 1, 2, 4, 6, 8, 10, and 12 hours postdose (postdose blood samples should be collected before the second administration of study drug); C1D22 and C2D1 predose of first administration.

h: Urine samples for PK analyses of tazemetostat will be collected in C0D1 at predose, 0-24, 24-48 and 48-72 hours postdose; C1D15 at 0-12 hours postdose of first administration.

i: The data of tumor assessments before informed consent within 28 days from study drug administration can be used as screening data if it meets the requirement of the protocol. Perform tumor assessment at screening, every 8 weeks [ $\pm$ 1 week] (starting at Cycle 1 Day 1) during Cycles 2-6, every 12 weeks [ $\pm$  1 week] starting at Cycle 7 and beyond, and discontinuation. The data within 28 days can be used as discontinuation data.

j: The data of bone marrow aspiration or biopsy before informed consent within 42 days from study drug administration can be used as screening data if it meets the requirement of the protocol. After the study drug dosing, perform bone marrow aspiration or biopsy if the result of screening was positive or unconfirmed and when to confirm CR as best of response or if clinically indicated.

k: Subjects should not take study drug before evaluations are performed (except tumor assessments and peripheral blood smear morphology assessment), unless specified.

l: Submit pre-study drug treated tumor sample to central laboratory before final observation, as far as possible.

m: Informed consent should be obtained before initiating the study or before entering the Extension Phase when Cycle 2 or later administrations will be continued.

n: In Cycle 13 or later, visits and assessments on Day 15 can be omitted at the discretion of the investigator or subinvestigator, if there was no concern for safety of the subject.

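### Does the lack of a scheduled visit between C1D22 and C2D1 leave late dose-limiting toxicities uncounted?

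*Protocol*

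**What the plan says.** Protocol 9.1.2 ties the primary endpoint to a fixed period: "The tolerability of tazemetostat will be determined based on the incidence of DLTs in Cycles 0 and 1". The first three subjects must be "evaluable for dose-limiting toxicities (DLTs) at the end of Cycle 1 of the cohort". Cycle 1 lasts 28 days (9.1.1.2). The DLT Analysis Set in Protocol 9.7.1.2 and SAP 5.2.1 uses the same two cycles.

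Table 6 places hematology, chemistry, physical examination and vital signs on Cycle 1 Days 1, 8, 15 and 22, then on C2D1. Two footnotes matter. One reads "c: +1 day for C2D1", so that visit may be late but not early. The other says "Subjects should not take study drug before evaluations are performed", with exceptions for tumor assessment and blood smear morphology. The rows for adverse events and concomitant therapy run without a break from consent to final observation.

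Four Table 1 criteria require more than 7 days, among them the one that begins "Other Grade 3 toxicity lasting". Others, such as Grade 4 thrombocytopenia, carry no duration.

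In 9.1.2, a DLT in 0 or 1 of 6 subjects makes the dose tolerable, 2 of 6 goes to a joint decision, and once "3 subjects in total experienced DLTs, the enrollment in the cohort will be discontinued". Where it is hard to say "whether a subject should be counted as having experienced a DLT and/or not for tolerability assessment", the investigator and sponsor decide together and may consult the Independent Data Monitoring Advisor.

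**The concern.** A window that closes on Day 28 with no visit at its close looks like a hole in the primary endpoint. It could matter in two ways.

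- **Dating.** An asymptomatic fall in platelets after C1D22 is first measured at C2D1. It arose under Cycle 1 treatment, but the sample carries a Cycle 2 date. If onset is taken from the sample date, the event drops out of Cycles 0 and 1.
- **Duration.** A toxicity that starts on Day 22 or later cannot exceed 7 days by Day 28. If duration must be completed inside the window, it can never be a DLT.

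With six subjects, one reclassified event can move 1 of 6 (tolerable) to 2 of 6 (joint decision), or 2 DLTs to 3 (enrolment stops). The study is open-label, hospitalization is required only to C1D15, and the one DLT reported abroad (Protocol 7.3.3) was Grade 4 thrombocytopenia, which SAP Appendix 13.1 defines by platelet count.

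**Working it through.** The plan gives no operating characteristic to reproduce: Protocol 9.7.2 says the sample size is not statistically based. The check is day arithmetic with C1D1 as Day 1, followed by two illustrations.

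**1. End of the window.** 28 days × 2 doses = 56, and 42/56 = 75%. This matches the compliance line in Table 1 and confirms a Day 28 close.

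**2. Unsampled days.** C1D22 (±1) is Day 21 to 23. Days left are 28 − 21 = 7, 28 − 22 = 6 and 28 − 23 = 5, which is 25.0%, 21.4% and 17.9% of Cycle 1. C2D1 is Day 29 or 30. The interval from C1D22 is 29 − 22 = 7 days nominally, from 29 − 23 = 6 to 30 − 21 = 9.

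**3. Duration.** To exceed 7 days by Day 28, onset must fall by Day 21 counting days inclusively (28 − 21 + 1 = 8), or by Day 20 counting elapsed days (28 − 20 = 8). Later onsets fail whatever the visit schedule, so an added Cycle 1 visit would not help. A toxicity first seen at C1D15 may sit exactly at 7 days at C1D22 (5 to 9 with windows), but if it is still present at C2D1 it has lasted 29 − 15 = 14 days.

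**4. What each kind of criterion relies on.**

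| Table 1 element | Source of evidence after C1D22 |
|---|---|
| Febrile neutropenia, bleeding, transfusion, growth-factor use | Continuous adverse event and concomitant therapy records |
| Nausea, vomiting, diarrhea; laboratory abnormality with symptoms | Continuous adverse event records; follow-up supplies duration |
| Grade 4 thrombocytopenia (no duration) | Any unscheduled count, otherwise the pre-dose C2D1 sample |
| Grade 4 neutropenia for more than 7 days | Samples at C1D22, C2D1 and later, or unscheduled counts |
| Other Grade 3 toxicity for more than 7 days | Adverse event dates; samples if purely a laboratory finding |

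Only the neutropenia criterion is both purely laboratory-based and duration-based. Protocol 9.5.1.5.1 follows adverse events to resolution or final observation, so durations that run past Day 28 will be on record. Protocol 9.7 places all analyses after database lock, when that follow-up is complete.

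**5. Scale of the late laboratory case (illustration).** Protocol 7.4 reports related Grade 3 or 4 thrombocytopenia in 2 of 46 subjects at 800 mg BID. Assume every such event begins in Cycle 1, with onset evenly spread. Per subject, 2/46 × 6/28 = 0.9%. For any of six, 1 − (1 − 0.0093)^6 = 5.5%. With 5 or 7 unsampled days the result is 4.6% or 6.3%. This includes Grade 3 events, which are DLTs only with bleeding or platelet transfusion, and it rests on two events in foreign patients. It is the chance that an event falls in those days, not the chance that it is missed.

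**6. Worst case if late DLTs were ignored.** P(0 or 1 of 6) = (1 − q)^6 + 6q(1 − q)^5, where q = true rate × (1 − share missed). The documents give neither quantity, so both are assumed:

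| True DLT rate | None missed | 10% missed | 20% missed |
|---|---|---|---|
| 20% | 0.655 | 0.704 | 0.753 |
| 30% | 0.420 | 0.487 | 0.558 |
| 40% | 0.233 | 0.301 | 0.378 |

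The last column is close to losing every DLT with onset in the six unsampled days (6/28 = 21.4% under even onset). No sentence in either document produces that loss.

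**The case for a change.** The best case for a change is that the rule is unwritten and would be cheap to write. The joint-determination clause names who decides, not which data count or when the three- and six-subject counts close. The decision would be taken with the result known, on a primary endpoint where one event matters. If everyone would count a pre-dose C2D1 finding, a sentence could record it.

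The facts stand: there is no sample between C1D22 and C2D1, and no attribution sentence. The inference that the count is therefore unsound does not. It needs onset to be dated by the sample and duration to be cut off at Day 28, and the documents state neither. The mention of Day 28 in the analysis-set definition concerns exclusions for poor compliance, not when a DLT begins or is confirmed. Evaluability is judged at the end of Cycle 1, and a visit that cannot be early and whose evaluations precede dosing is the natural close of that cycle. The foreign DLT occurred at 1600 mg BID, twice the dose here. A move from 1 to 2 of 6 also needs a DLT in another subject.

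A written rule would not be neutral either. Whether a finding is a Cycle 1 DLT also decides whether Protocol 9.4.1.1.1 or 9.4.1.1.2 governs the subject's treatment, and the two differ. That is a clinical matter on which I take no view.

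**Conclusion.** No change follows. This is a small gap in detail that the people doing the count can fill sensibly from what is already there: events dated by onset, the pre-dose C2D1 evaluation read as the close of Cycle 1, durations taken from adverse event follow-up, and joint determination for the remainder. Its extent is 6 of 28 days without a scheduled sample. It bears chiefly on asymptomatic laboratory findings and on toxicities starting on about Day 22 or later. The thrombocytopenia illustration gives about 5.5% (4.6% to 6.3%) for any of six subjects, under the assumptions stated with it.

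The conclusion assumes that onset and end dates are recorded for events straddling Day 28, and that any joint determination is documented. SAP section 9 places derivation rules in separate documents, which were not available. If those rules dated DLTs by sample or cut durations at Day 28, the worst-case table would become relevant. Nothing in the Protocol or SAP points that way.
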